7.4 Growth Factors

Growth factors that support platelet or white cell number or function can only be administered for culture proven bacteremia or invasive fungal infection. The Study Chair should be notified before growth factors are initiated.

7.5 Concomitant Medications**7.5.1 CYP3A4 substrates, inhibitors or inducers:**

In vitro data showed that LY3023414 is a substrate of CYP3A4 and CYP1A2 (to a lesser extent). Therefore, moderate to strong inducers and strong inhibitors of CYP3A4 should be substituted or avoided, if possible. (See [Appendix II](#)). However, in patients for whom there are no adequate therapeutic alternatives, CYP3A4 inducing anti-epileptic drugs and dexamethasone for CNS tumors or metastases, on a stable dose, are allowed.

LY3023414 is a weak inhibitor of CYP3A4. Monitor patients receiving drugs that are either sensitive substrates of CYP3A4 or CYP3A4 substrates with a narrow therapeutic range.

7.5.2 Strong inducers (eg., smoking) and inhibitors (eg., ciprofloxacin, enoxacin, fluvoxamine, zafirlukast) of CYP1A2 should also be avoided if possible while receiving protocol therapy.

8.0 EVALUATIONS/MATERIAL AND DATA TO BE ACCESSIONED

8.1 Required Clinical, Laboratory and Disease Evaluation

All clinical and laboratory studies to determine eligibility must be performed within 7 days prior to enrollment unless otherwise indicated. Laboratory values used to assess eligibility (see [Section 4.0](#)) must be no older than seven (7) days at the start of therapy. Laboratory tests need **not** be repeated if therapy starts **within** seven (7) days of obtaining labs to assess eligibility. If a post-enrollment lab value is outside the limits of eligibility, or laboratory values are older than 7 days, then the following laboratory evaluations must be re-checked within 48 hours prior to initiating therapy: CBC with differential, bilirubin, ALT (SGPT) and serum creatinine. If the recheck is outside the limits of eligibility, the patient may not receive protocol therapy and will be considered off protocol therapy. Imaging studies, bone marrow aspirate and/or biopsy, must be obtained within 14 days prior to start of protocol therapy (repeat the tumor imaging if necessary).

STUDIES TO BE OBTAINED	Pre-Study	During Cycle 1	Prior to Subsequent Cycles [^]
History	X	Weekly	X
Physical Exam with vital signs	X	Weekly	X
Neurologic Exam	X	Weekly	X
Height, weight, BSA	X		X
Performance Status	X		
Pregnancy Test ¹	X		
CBC, differential, platelets	X	Twice Weekly (every 3 to 4 days) ²	Weekly ³
Urinalysis	X		
Electrolytes including Ca ⁺⁺ , PO ₄ , Mg ⁺⁺	X	Weekly	X
Creatinine, ALT, bilirubin	X	Weekly	X
Glucose	X	Weekly	X
Albumin	X		X
Total cholesterol, triglycerides	X		X
Tumor Disease Evaluation ^{4A}	X		Every other cycle ⁴
Bone Marrow Aspirate and/or biopsy ^{5,6}	X ⁵		Every other cycle ⁶
EKG	X		
Medication Diary ⁷		Weekly	X
Pharmacokinetics (optional) ⁸	X	X	
Circulating Tumor DNA (ctDNA-optional) ⁹			Cycle 5, Day 1 and (for patients receiving \geq 5 cycles only) at end of protocol therapy OR disease progression

[^] Studies may be obtained within 72 hours prior to the start of the subsequent cycle.

¹ Women of childbearing potential require a negative pregnancy test prior to starting treatment; sexually active patients must use an acceptable method of birth control. Abstinence is an acceptable method of birth control.

² If patients have Grade 4 neutropenia then CBCs should be checked at least every other day until recovery to Grade 3 or until meeting the criteria for dose limiting toxicity.

³ If patients develop Grade 4 neutropenia then CBCs should be checked every 3 to 4 days until recovery to Grade 3

^{4A} Neurological exam also required for CNS patients.

- ⁴ Tumor Disease Evaluation should be obtained on the next consecutive cycle after initial documentation of either a PR or CR. Subsequent scans may restart 2 cycles after the confirmatory scan. If the institutional investigator determines that the patient has progressed based on clinical or laboratory evidence, he/she may opt not to confirm this finding radiographically.
- ⁵ Bone marrow aspirate and/or biopsy only required in patients suspected of having bone marrow metastasis on the basis of history, symptoms, laboratory evaluation or other clinical data.
- ⁶ Bone marrow aspirate and/or biopsy should only be performed on patients with known bone marrow involvement at baseline
- ⁷ Patient diary (see [Appendix III](#)) should be reviewed after completion of each treatment cycle and uploaded into RAVE.
- ⁸ See [Section 8.3](#) for details of PK studies.
- ⁹ With consent, two samples will be collected on this protocol (cycle 5 Day 1; and for patients receiving ≥ 5 cycles only: at progression or end of protocol therapy) see [Section 8.4](#) for details of the ctDNA studies. Note that a ctDNA sample is scheduled to be obtained on the APEC1621SC screening protocol prior to the initiation of treatment on this subprotocol.

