4.1.7 Organ Function Requirements

4.1.7.1 Adequate Bone Marrow Function Defined as:

- a. For patients with solid tumors without known bone marrow involvement:
 - Peripheral absolute neutrophil count (ANC) $\geq 1000/\text{mm}^3$
 - Platelet count $\geq 100,000/\text{mm}^3$ (transfusion independent, defined as not receiving platelet transfusions for at least 7 days prior to enrollment)
- b. Patients with known bone marrow metastatic disease will be eligible for study provided they meet the blood counts in [Section 4.1.7.1.a](#) (may receive transfusions provided they are not known to be refractory to red cell or platelet transfusions). These patients will not be evaluable for hematologic toxicity.

4.1.7.2 Adequate Renal Function Defined as:

- Creatinine clearance or radioisotope GFR $\geq 70\text{ml/min}/1.73\text{ m}^2$ or
- A serum creatinine based on age/gender as follows:

Age	Maximum Serum Creatinine (mg/dL)	
	Male	Female
1 to < 2 years	0.6	0.6
2 to < 6 years	0.8	0.8
6 to < 10 years	1	1
10 to < 13 years	1.2	1.2
13 to < 16 years	1.5	1.4
≥ 16 years	1.7	1.4

The threshold creatinine values in this Table were derived from the Schwartz formula for estimating GFR utilizing child length and stature data published by the CDC.⁵⁸

4.1.7.3 Adequate Liver Function Defined as:

- Bilirubin (sum of conjugated + unconjugated) $\leq 1.5 \times$ upper limit of normal (ULN) for age
- SGPT (ALT) $\leq 135\text{ U/L}$. (For the purpose of this study, the ULN for SGPT is 45 U/L.)
- Serum albumin $\geq 2\text{ g/dL}$.

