5.4 Definition of Dose-Limiting Toxicity (DLT)

DLT will be defined as any of the following events that are possibly, probably or definitely attributable to protocol therapy. Dose limiting hematological and non-hematological toxicities are defined differently.

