5.4.2 Hematological dose limiting toxicity

5.4.2.1 Hematological dose limiting toxicity is defined as:

- a) In patients evaluable for hematological toxicity (see [Section 4.1.7.1](#)),
 - Grade 4 thrombocytopenia or neutropenia, not due to malignant infiltration.
 - Grade 3 thrombocytopenia that persists for ≥ 7 days
 - Grade 3 thrombocytopenia requiring a platelet transfusion on two separate days within a 7-day period
 - Grade 3 thrombocytopenia with clinically significant bleeding
 - Neutropenia or thrombocytopenia that causes a delay of > 14 days between treatment cycles.

5.4.2.2 Note: Grade 3 or 4 febrile neutropenia will not be considered a dose-limiting toxicity.

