6.1 Dose Modifications for Hematological Toxicity

- 6.1.1 If a patient experiences hematological dose-limiting toxicity as defined in [Section 5.4.2](#), the treatment will be held. Counts should be checked every 3-4 days for thrombocytopenia and every other day for neutropenia during this time. If the toxicity resolves to meet eligibility parameters within 14 days of drug discontinuation, the patient may resume treatment at a reduced dose as outlined in the dose reduction table ([Appendix IV](#)). Doses reduced for toxicity will not be re-escalated, even if there is minimal or no toxicity with the reduced dose.
- 6.1.2 If toxicity does not resolve to meet eligibility parameters within 14 days of drug discontinuation, the patient must be removed from protocol therapy.
- 6.1.3 If hematological dose-limiting toxicity recurs in a patient who has resumed treatment at the reduced dose, the patient must be removed from protocol therapy.

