- f. CBC/differential/platelets- If patients have Grade 4 neutropenia then CBCs should be checked at least every other day until recovery to Grade 3 or until meeting the criteria for dose limiting toxicity.
- g. Urinalysis
- h. Electrolytes including Ca++, PO4, Mg++
- i. Creatinine, ALT, bilirubin; Glucose
- j. Albumin; Total cholesterol, triglycerides
- k. Tumor Disease Evaluation
- l. Bone Marrow Aspirate and/or biopsy- At baseline, only required for patients suspected of having bone marrow metastasis on the basis of history, symptoms, laboratory evaluation or other clinical data.
- m. Patient Diary- (see [Appendix III](#)) should be reviewed after completion of each treatment cycle and uploaded into RAVE. The patient diary should be collected weekly.
- n. Pharmacokinetics- see [Section 8.3](#) for details of PK studies.
- o. EKG

Cycle 1

This listing only includes evaluations necessary to answer the primary and secondary aims. OBTAIN OTHER STUDIES AS REQUIRED FOR GOOD CLINICAL CARE.

Comments

(Include any held doses, or dose modifications)

All Subsequent Cycles

Therapy Delivery Map – All Subsequent Cycles

This Therapy Delivery Map (TDM) relates to all subsequent cycles. Each cycle lasts 28 days. Treatment may continue in the absence of disease progression or unacceptable toxicity. Use a copy of this page once for each cycle (please note cycle number below).

Patient COG ID number

Accession number

Criteria to start each cycle are listed in [Section 5.2](#). Extensive treatment details are in [Section 5.1](#).

DRUG	ROUTE	DOSAGE	DAYS	IMPORTANT NOTES
LY3023414 IND # 134661	PO	Dose Level 2: 115 mg/m ² /dose BID (Recommended Phase 2 Dose) Refer to dosing nomogram in Appendix IV .	1-28	LY3023414 should be taken without regards to food with a glass of water at approximately the same time each day. Patients should swallow the tablets as a whole and should not chew or crush them. If a patient misses a dose of LY3023414, the dose should be taken as soon as possible as long as it is more than 6 hours before the next scheduled dose. If it is less than 6 hours before the next dose, then the dose should be skipped. If vomiting occurs after taking LY3023414, the patient should skip the dose and take the next dose as scheduled.

Enter Cycle #: _____ Dose Level: _____ Ht _____ cm Wt _____ kg BSA _____ m²

Date Due	Date Given	Day	LY3023414 mg AM mg PM	Studies
			Enter calculated dose above as per dosing nomogram and actual dose administered below	

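### After cycle 1, the evaluation table and delivery map ask for fewer neutrophil counts, with an earlier stopping point, than Section 6.1.1 requires during a DLT hold for Grade 4 neutropenia

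*Combined protocol and SAP*

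**What the plan says.** Four parts of the protocol bear on this.

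- **What counts as a DLT.** Section 5.4 states: "DLT will be defined as any of the following events that are possibly, probably or definitely attributable to protocol therapy". For patients evaluable for hematological toxicity, 5.4.2.1 lists "Grade 4 thrombocytopenia or neutropenia, not due to malignant infiltration", with no minimum duration. Section 4.1.7.1 takes patients with known marrow metastases out of this group: "These patients will not be evaluable for hematologic toxicity".
- **What happens at a hematological DLT.** Section 6.1.1 holds treatment and adds: "Counts should be checked every 3-4 days for thrombocytopenia and every other day for neutropenia during this time". Treatment may resume at a reduced dose once eligibility parameters are met within 14 days; the neutrophil level in 4.1.7.1 is an ANC of at least 1000/mm³. Section 6.1.2 covers failure: "If toxicity does not resolve to meet eligibility parameters within 14 days of drug discontinuation, the patient must be removed from protocol therapy".
- **Cycle 1 schedule.** Item f of the cycle 1 delivery map in Appendix VI says "If patients have Grade 4 neutropenia then CBCs should be checked at least every other day until recovery to Grade 3". Footnote 2 of 8.1 sets the same interval, and its end point reads "until recovery to Grade 3 or until meeting the criteria for dose limiting toxicity".
- **Later-cycle schedule.** Footnote 3 of 8.1 says "If patients develop Grade 4 neutropenia then CBCs should be checked every 3 to 4 days until recovery to Grade 3". Item c of the subsequent-cycles map in Appendix VI uses the same words.

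**The concern.** The same patient can fall under two instructions. If Grade 4 neutropenia appears in cycle 2 or later and meets the DLT definition, 6.1.1 asks for counts every other day. The table and map that sites work from ask for counts every 3 to 4 days, which is the interval 6.1.1 gives for thrombocytopenia. They also end the closer checks at Grade 3, whereas the resume-or-remove decision turns on eligibility levels.

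At stake are safety monitoring during severe neutropenia and the evidence for a mandatory removal. A patient who recovers just inside 14 days may have no count that shows it in time. Section 7.4 limits white-cell growth factors to culture-proven bacteremia or invasive fungal infection, so holding drug and following counts are the main tools the protocol leaves for this event.

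**Working it through.** The plan gives no figure to reproduce. The check is a comparison of texts followed by a count of scheduled draws.

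**1. Does 6.1.1 apply after cycle 1?** Yes. Section 6.1 has no cycle limit. Sections 5.1.1 and 11.2.2 restrict only the dose-escalation decision to cycle 1, and 11.6 recognises a DLT at any time during protocol therapy. With a maximum of 6 cycles (5.1), the later-cycle schedule covers up to five of them.

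**2. Do the instructions meet in the same patient?** Yes, when three conditions hold: the patient is evaluable for hematological toxicity, the neutropenia is at least possibly attributable to LY3023414, and it is not due to malignant infiltration. Because 5.4.2.1 has no duration criterion for Grade 4 neutropenia, the hold starts as soon as the event is recognised. Outside these conditions, footnote 3 conflicts with nothing.

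| | 6.1.1 | 8.1 footnote 3 and Appendix VI item c |
|---|---|---|
| Interval for neutropenia | every other day | every 3 to 4 days |
| End point | eligibility level, 14-day limit | Grade 3 |

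**3. Counts in a 14-day hold.** Take day 0 as the day drug is held, with the first follow-up count one interval later. The number of counts by day 14 is 14 divided by the interval, rounded down.

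| Spacing | Count days | Counts by day 14 | First count at or after recovery on day 13 or 14 |
|---|---|---|---|
| 2 days | 2, 4, 6, 8, 10, 12, 14 | 7 | 14 |
| 3 days | 3, 6, 9, 12, then 15 | 4 | 15 |
| 4 days | 4, 8, 12, then 16 | 3 | 16 |
| alternating 3, 4 | 3, 7, 10, 14 | 4 | 14 |
| alternating 4, 3 | 4, 7, 11, 14 | 4 | 14 |

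The later-cycle schedule therefore yields 3/7 = 43% to 4/7 = 57% of the counts that 6.1.1 asks for.

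**4. How often is day 14 missed?** Take every mix of 3- and 4-day steps and group the patterns by their last count on or before day 14:

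- Day 14 needs two 3s and two 4s: 4!/(2!·2!) = 6 patterns.
- Day 13 needs three 3s and one 4: 4 patterns.
- Day 12 is 3-3-3-3 or 4-4-4: 2 patterns.
- Day 11 is one 3 and two 4s, followed by a 4-day step to day 15: 3 patterns.

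The total is 6 + 4 + 2 + 3 = 15. Nine patterns have no day-14 count, so they miss a recovery that occurs on day 14. Five of those nine (last count on day 11 or 12) also have no day-13 count, so they miss a recovery on day 13 as well. These are numbers of possible patterns, not probabilities.

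**5. If closer checks stop at Grade 3.** Step 4 assumes the 3-to-4-day checks run through the whole hold. Read literally, footnote 3 ends them at Grade 3, leaving the table's weekly count. If Grade 3 is first documented on hold day d, a count 7 days later falls on day d + 7, which is after day 14 whenever d is 8 or more. A site that keeps a fixed weekly day could still happen to land on day 14.

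**The case against.** There is a fair case that this matters little. The 14-day limit and the every-other-day instruction sit together in 6.1.1, so a site that applies the limit has very likely read the interval. Section 6.1.1 is specific to a hold, while footnote 3 sits in a routine evaluation table, and the specific rule would naturally govern. Section 5.3 requires any suspected DLT to be reported to the Study Chair within 24 hours. The later-cycle map tells sites to obtain further studies that good care requires, so a day-14 draw is never barred. Routine counts also step down from twice weekly to weekly after cycle 1, so a lighter Grade 4 interval could be a deliberate taper.

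The event also looks rare. In 9.1.9 (165 patients), decreased neutrophil count is listed among events with insufficient evidence of causation. The adult phase 1 DLTs described in 2.3.1 include no neutropenia, and 5.1.1 reports no cycle 1 DLTs at either pediatric dose level.

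The rarity argument stands and limits the impact. The rest lowers the chance of error without removing the conflict. A taper explains fewer counts for a patient on drug, but not fewer during a DLT hold, where 6.1.1 makes no distinction by cycle. Notifying the Study Chair does not correct the printed schedule, and no sentence gives 6.1.1 precedence.

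**Conclusion.** The concern holds. For DLT-qualifying Grade 4 neutropenia after cycle 1, footnote 3 and map item c contradict 6.1.1 on both the interval and the end point. The cycle 1 texts already use the every-other-day interval, so the later-cycle wording is the one out of line.

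Following the later-cycle wording gives 3 or 4 counts instead of 7 over a full hold, and recovery on day 13 or 14 may be documented too late. That late documentation is possible, not certain: it depends on the spacing a site chooses and assumes no extra draw is made for the day-14 decision.

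The reach is small: a subset, probably a very small one, of at most 24 planned patients (11.1). The 20-patient response rule and the completed dose finding are untouched. The correction should be made because it affects safety monitoring and a mandatory removal, and it costs little.

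**What to change.** In 8.1 footnote 3 and Appendix VI item c (subsequent cycles), state that Grade 4 neutropenia meeting 5.4.2 is managed under 6.1.1: counts every other day until eligibility parameters are met, including a count by day 14 of the hold. Keep the 3-to-4-day interval only for Grade 4 neutropenia that is not a DLT, such as in patients not evaluable for hematological toxicity.

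A smaller clarification belongs with it. Footnote 2 and cycle 1 map item f offer reaching DLT criteria as a stopping point for the closer checks. In evaluable patients, attributable Grade 4 neutropenia not due to infiltration is already a DLT, so that clause should be replaced by a pointer to 6.1.1.

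The cost is wording in two footnotes and two map items, plus 7 − 4 = 3 to 7 − 3 = 4 more blood counts per patient over a full 14-day hold than the later-cycle schedule gives. Section 6.1.1 already calls for those counts.

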8.2 Radiology Studies

8.2.1 **Central Radiology Review for Response:** Patients who respond (CR, PR) to therapy or have long term stable disease (SD) (6 cycles) on protocol therapy will be centrally reviewed.

8.2.2 **Technical Details of Submission:**

To ensure an adequate interpretation of FDG-PET and CT with contrast scans, scans transferred between the treating institutions and the Imaging and Radiation Oncology Core Group IROC RI (QARC) must be submitted in Digital Imaging and Communications in Medicine (DICOM) format. BMP files, JPG files, or hard copies (films) are unacceptable for adequate interpretation of PET and CT with contrast scans. Imaging studies must be submitted electronically as outlined in the following paragraph. The images will be made available to study radiologists and nuclear medicine physicians for central review.

Submission of Diagnostic Imaging data in digital format is required. Digital files must be in DICOM format. Due to the critical time constraints for submitting data for the central review of response the following methods should be used to submit imaging data, such as sFTP, Dicommunicator, or on CD (if sent by courier). Digital data submission instructions including instructions for obtaining a sFTP account, can be found at <http://irocri.qarc.org>. Follow the link labeled digital data. Alternatively, if submission via sFTP or Dicommunicator is not feasible, the imaging may be burned to a CD and mailed to IROC RI (QARC) at the address below. Multiple studies for the same patient may be submitted on one CD; however, please submit only one patient per CD. Sites using Dicommunicator may submit imaging via that application. Contact IROC RI (QARC) with questions or for additional information.

For FDG-PET imaging, the transferred imaging data should include uncorrected and attenuation-corrected PET projection data, as well as the reconstructed PET or PET/CT images used by the institution to achieve a response assessment. If low-dose CT was used for attenuation correction, the acquired CT images should also be submitted. The imaging data submitted for central review must allow the study to be reconstructed and displayed in transaxial, sagittal and coronal formats using

standard reconstruction techniques. Reconstructed MPEG clips and similar types of reconstructions will not be accepted. CT and MRI images similarly should be submitted in a format that either includes properly reconstructed multi-planar viewing formats in soft tissue and bone windows, or includes the thin-section axial acquisition data from which multi-planar reconstructions can be re-created.

Address for submission: IROC RI (QARC)
[name]
[name]
[contact]
[contact]
Web: <http://irocri.qarc.org>

8.3 Pharmacology (optional)

8.3.1 Description of Studies and Assay

Pharmacokinetics (PK) will be performed to determine the PK of LY3023414 in children who consent to this optional study. Pharmacokinetic analysis will be conducted at a centralized laboratory using validated assays.

8.3.2 Sampling Schedule

Blood samples will be obtained at the following time points **for ALL patients enrolled on study who consent to optional pharmacokinetics:**

- **Day 15, Cycle 1:** Pre-dose (12 hours after the PM dose on Day 14, Cycle 1) and at 1-2 hours after the AM dose on Day 15.

Determination of the recommended phase 2 dose is complete. Blood samples will were obtained at the following time points **ONLY for patients enrolled during the determination of the recommended phase 2 dose / tolerable dose (Section 5.1.1) who consented to optional pharmacokinetics**

- **Day 1, Cycle 1:** Pre-dose, and at 30 minutes, 1, 2, 4, 6-8 hours after the AM dose on Day 1. **The PM dose of LY3023414 on Day 1, Cycle 1 will not be given for patients undergoing these PK studies.**
- **Day 2, Cycle 1:** Before the AM dose on Day 2 (24 hours after the AM dose on Day 1, Cycle 1).

8.3.3 Sample Collection and Handling Instructions

Blood samples (2 ml for each time point) will be collected in K₂-EDTA (lavender top) tubes for pharmacokinetic evaluation. Record the exact time that the sample is drawn along with the exact time that the drug is administered.

Sites are expected to use their own standard materials for PK sample collection as kits will not be provided for the PK samples for this study.

